6.1.7. Informed Consent

In this study, all patients will be asked to provide separate written informed consent for Part 1 and for Part 2 of the study, even if adjuvant cemiplimab is not administered in Part 2. Written consent for Part 1 must be obtained before the first dose of neoadjuvant cemiplimab (see [Table 2](#) for window). Written consent for Part 2 must be obtained prior to any adjuvant treatment or assessments (see [Table 3](#) or window). Informed consent for Part 2 is meant to ensure that all study patients are informed of their treatment options (adjuvant cemiplimab, radiation-based treatment, or observation). The risks and benefits regarding each option may be influenced by the outcome of Part 1, and therefore a separate consenting process in Part 2 is required.

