- Patients who receive adjuvant radiation therapy or enter observation only during Part 2 of the study will follow a parallel imaging schedule as described in [Section 9.1.6](#).
- The window for treatment visits is ± 3 days. In the event of a missed dose, patients will not be allowed to receive the scheduled cemiplimab dose outside of this window. Any missed doses will result in a reduction in the total number of allowable doses that may be administered.

Table 2: Schedule of Events for Screening, Neoadjuvant Cemiplimab, and Surgery (Part 1 of the Study)

Study Procedure	Screening/ Baseline ¹	Cemiplimab Treatment				Surgery	EOT1 (or Early Termination) ³
		1	22±3	43±3	64±3		
Visit Days	-28 to -1					85 (75 to 100)	30 days ± 10 after surgery
Informed Consent ²	X						
Clinical Assessments							
Medical History/Oncology History	X						
Complete Physical Examination and ECOG PS	X						X
Limited Physical Examination		X	X	X	X		
Vital Signs and Weight	X	X ⁴	X ⁴	X ⁴	X ⁴		X
Height	X						
12-Lead ECG	X						X
Laboratory Tests							
Hematology ⁵	X	X	X	X	X		X
Blood Chemistry ⁵	X	X	X	X	X		X
Pregnancy Test for WOCBP ⁶	X	X	X	X	X		X
Urinalysis	X						X
HBV, HCV, HIV	X						
INR, aPTT ⁷	X					X	
TSH (with reflex T3, free T4) ⁸	X						X
Treatment							
Cemiplimab 350 mg IV Q3W		X	X	X	X		
Surgery ⁹						X	
Response Assessment							
CT/MRI ¹⁰	X			X		X	X
Digital Photography ¹⁰	X			X		X	
Tumor Biopsy ¹¹	X		X				
Treatment Management Plan Assessment ¹²	X				X		
PD/Biomarker Analysis							
PBMC Immune Monitoring Sample		X	X				
Plasma ctDNA Sample	X						X
Whole Blood Genomic DNA (mandatory)	X ¹³						
Whole Blood Genomic DNA (optional sub-study)		X ¹⁴					
Immunogenicity							
ADASample ¹⁵		X				X	X
Patient Reported Outcomes							
EORTC-QLQ-C30 ¹⁶	X					X	

Other Assessments	
Concomitant Medications	← continuous monitoring →
Adverse Events	← continuous monitoring →

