ADA=anti-drug antibody; aPTT=activated partial thromboplastin time; CT=computed tomography; ctDNA=circulating tumor deoxyribonucleic acid; DNA= deoxyribonucleic acid; ECG=electrocardiogram; ECOG PS=Eastern Cooperative Oncology Group Performance Status; EORTC QLQ-C30= European Organization for Research and Treatment of Cancer Quality of Life Questionnaire-Core 30; EOT1=end of treatment in Part 1 (neoadjuvant); HBV=hepatitis B virus; HCV=hepatitis C virus; HIV=human immunodeficiency virus; INR=international normalized ratio; IV=intravenous; MRI=magnetic resonance imaging; PBMC=peripheral blood mononuclear cells; PD=pharmacodynamic; Q3W=every 3 weeks; TSH=thyroid-stimulating hormone; WOCBP=women of childbearing potential

9.1.1. Footnotes for Table 2: Schedule of Events for Screening, Neoadjuvant Cemiplimab, and Surgery (Part 1 of the Study)

- All screening assessments must be performed within 28 days prior to the first dose of neoadjuvant cemiplimab. Assessments performed as part of standard of care that fall within the screening window, but before informed consent is obtained, may be used for screening, and need not be repeated for enrollment eligibility. If complete physical examination, hematology, blood chemistry, and/or pregnancy assessments were completed as part of screening and occurred within 3 days of the first neoadjuvant dose, these procedures may be waived during the first-dose visit.
- Informed consent for Part 1 must be provided before the initiation of screening procedures and must be obtained within 28 days prior to the first dose of neoadjuvant cemiplimab.
- All patients will undergo an EOT1 visit after surgery. At the EOT1 visit, patients will be given the opportunity to consent to Part 2. See Section 9.1.5.1 for guidance regarding patients who discontinue early in Part 1.
- At cemiplimab treatment day 1, vital signs will be collected prior to infusion and approximately 30 minutes after the completion of the infusion. For all other treatment days, vital signs are collected prior to infusion and approximately 15 minutes after the completion of the infusion. The allowable window for each specified time point is ± 10 minutes.
- Hematology and chemistry samples may be obtained ≤ 72 hours prior to cemiplimab treatment.

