- Pregnancy testing at screening must be serum β -HCG for pre-dose samples up to 72 hours prior to first administration. Subsequent predose pregnancy tests (up to 72 hours before each dose of cemiplimab) may be urine β -HCG. Serum pregnancy test and urine pregnancy test are requirements for women of child bearing potential only. If surgical procedure for sterility was done ≤ 30 days prior to signing ICF, serum pregnancy test must still be performed.
- Coagulation tests (PT/aPTT) will be performed during screening and in the pre-operative period (within 10 days prior to surgery).
- If TSH is abnormal, a T3 and free T4 should be measured by the site's local laboratory.

9. Surgery will occur after posttreatment imaging response assessment and should occur 21 days after the last dose of cemiplimab. The window for surgery is from day 75 through day 100. The eCRF will capture information concerning the surgical procedure performed and surgical findings. Tumor tissue from the surgical resection should be provided for pathologic assessment of neoadjuvant treatment response and for biomarker analysis. If feasible, tissue sample should be provided as a formalin-fixed paraffin-embedded (FFPE) block or 25 unstained slides and should also include an RNAlater[®] sample. Additional requirements for biomarker analysis will be described in the laboratory manual.
10. See Section 9.2.2.3 for imaging requirements, which include CT/magnetic resonance imaging (MRI) and digital photography. Imaging is performed at baseline, prior to the third dose of neoadjuvant cemiplimab, and prior to surgery. The window for imaging prior to the third dose is day 35 to day 46. Imaging taken prior to surgery may occur at any time during the protocol window for surgery (day 75 through day 100). Digital photography is mandatory at baseline imaging assessment and at the imaging assessment that occurs prior to surgery; photography at imaging assessment prior to the third dose is optional. Radiologic imaging is required at each imaging assessment. At EOT1, imaging is optional.

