Tumor Biopsy	At any time that disease recurrence or SPT is suspected ⁸				
PD/Biomarker Analysis					
Plasma ctDNA Sample				X	X
Immunogenicity					
ADA Sample ⁹		X		X	X
Patient-Reported Outcomes					
EORTC QLQ-C30				X ¹⁰	
Other Assessments					
Concomitant Medications	← continuous monitoring →				
Adverse Events	← continuous monitoring →				

ADA=anti-drug antibody; ctDNA=circulating tumor deoxyribonucleic acid; ECOG PS=Eastern Cooperative Oncology Group Performance Status; EORTC QLQ-C30= European Organization for Research and Treatment of Cancer Quality of Life Questionnaire-Core 30; EOT2=end of treatment in Part 2 (adjuvant); IV=intravenous; PD=pharmacodynamic; SPT=second primary tumor; Q3W=every 3 weeks; TSH=thyroid-stimulating hormone; WOCBP=women of childbearing potential

9.1.2. Footnotes for Table 3: Schedule of Events for Adjuvant Cemiplimab (Part 2 of the Study)

1. Patients who receive radiation therapy, or observation only, will undergo their first imaging assessment during the same time frame as patients who receive cemiplimab (week 15 of Part 2). Laboratory assessments and clinical assessments do not pertain to patients who receive radiation therapy or observation in Part 2, but all imaging assessments are required for all patients. See Section 9.1.6.
2. The first adjuvant cemiplimab dose should be administered at week 0 (3 weeks [± 3 days] after the EOT1 visit). If the initial dose does not occur within this window, adjuvant cemiplimab treatment may not be provided until week 3 of Part 2. In the event of a missed initial dose, patients must complete all assessments outlined under “first dose” during their first adjuvant treatment visit.
3. Evaluation visits should occur at week 15 of Part 2 (± 10 days), week 30 (± 10 days), and at EOT2 (21 to 37 days after the last dose) or at the early termination visit.
4. All patients must provide written informed consent for Part 2. This should be obtained at EOT1. If not obtained at EOT1, all patients must provide written consent prior to initiation of any adjuvant treatment or assessments.
5. Hematology panel is only required every 6 weeks. On these visits, labs may be obtained within 3 days of a planned cemiplimab dose.
6. Predose pregnancy tests (up to 72 hours before the dose) may be satisfied by either serum pregnancy test or by urine β -HCG. Pregnancy tests are performed prior to each dose of cemiplimab and at EOT2. Pregnancy tests are a requirement for WOCBP only.

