4.4.2. Secondary Efficacy Variables

The secondary efficacy variables include:

- Major pathologic response (mPR) rate per independent central pathology review: mPR is defined as failure to achieve pCR but $\leq 10\%$ viable cancer cells in the surgical pathology sample.
- pCR rate and mPR rate assessed by local pathology review: pCR and mPR will be assessed by local pathology review.
- Objective response rate (ORR) prior to surgery by investigator assessment: ORR is determined by the proportion of patients with CR or PR based on investigator-assessed evaluation using RECIST 1.1 (Eisenhauer, 2009), where there is no requirement for confirmation of CR or PR. The objective response will be measured from the first dose of neoadjuvant cemiplimab to surgery or any other new anti-cancer therapy.
- Event free survival (EFS) is defined as time from first dose of neoadjuvant cemiplimab to the first of any of the following events: progression of disease that precludes surgery, inability to undergo complete resection (R0 or R1), disease recurrence (local, regional, or distant) for patients who undergo complete resection (R0 or R1), or death due to any cause.
 - Patients who do not have an EFS event without initiation of a new anti-cancer therapy will be censored at the last evaluable tumor assessment.
 - Patients who do not have an EFS event but initiate a new anti-cancer therapy, will be censored at the last evaluable tumor assessment prior to or on the date of new anti-cancer therapy.
 - Patients who do not have any evaluable post-baseline tumor assessment and do not die will be censored on the date of first study treatment.
- Disease free survival (DFS) is defined for patients who are free of disease (R0 or R1 resection) at completion of surgery as time from date of surgery until first recurrence (local, regional, or distant) or death due to any cause.
 - Patients who do not have recurrence of tumor and alive without initiation of a new anti-cancer therapy will be censored at the last evaluable tumor assessment.

- Patients who do not have recurrence of tumor and alive, but initiate a new anti-cancer therapy, will be censored at the last evaluable tumor assessment prior to or on the date of new anti-cancer therapy.
- Patients who do not have any tumor assessment after surgery and do not die will be censored on the date of surgery.

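### All mandated recurrence imaging after surgery depends on a second consent sought once the surgical outcome is known, and no recurrence follow-up is defined for a patient who declines it without withdrawing

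*Protocol*

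**What the plan says.** Protocol Section 6.1.7 asks every patient for a separate Part 2 consent, including those who will take no adjuvant cemiplimab: "Written consent for Part 2 must be obtained prior to any adjuvant treatment or assessments". Table 3 footnote 4 (Section 9.1.2) repeats the rule: "If not obtained at EOT1, all patients must provide written consent prior to initiation of any adjuvant treatment or assessments".

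The timing is after surgery. Table 2 footnote 3 says "At the EOT1 visit, patients will be given the opportunity to consent to Part 2", and Table 2 places that visit at "30 days ± 10 after surgery". Section 6.1.7 gives the reason for a second consent: it is meant to inform patients of their treatment options, and "The risks and benefits regarding each option may be influenced by the outcome of Part 1".

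Mandatory recurrence imaging is scheduled only in Table 3 (weeks 15, 30 and 48/EOT2) and Table 4 (three further years). Before the Part 2 consent, Table 2 footnote 10 offers only this: "At EOT1, imaging is optional".

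SAP Section 4.4.2 censors EFS at the last evaluable tumor assessment. For DFS it adds: "Patients who do not have any tumor assessment after surgery and do not die will be censored on the date of surgery".

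**The concern.** EFS and DFS are secondary endpoints of neoadjuvant treatment. Section 4 of the protocol says both will be assessed until all enrolled patients have completed follow-up, about 4 years and 3 months. The consent rule makes recurrence observation conditional on a second agreement, given when the patient already knows how surgery went and is choosing among adjuvant options.

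The reason stated in Section 6.1.7 supports a fresh consent to adjuvant treatment. It gives no reason to ask again for permission to observe recurrence.

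Willingness to go on could be related to prognosis in either direction. A patient with a complete response may want no more visits; one with poor pathology may seek care elsewhere. Either would make the censoring informative, and nothing planned would show it. The SAP has no disposition line for patients who decline Part 2 (Section 5.4), plans no imputation (Section 6.3) and specifies no sensitivity analysis for this censoring.

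**Working it through.** **The plan's own figure.** The only design calculation is for pCR. It reproduces with the exact binomial: at n = 76, 28 responders (36.8%) give a 95% lower limit of 0.261 and 27 give 0.249. Exact power at a true rate of 44% is 93.0% at n = 72 and 91.6% at n = 76. The pCR result is fixed at surgery, so the second consent does not touch it. No assumption is stated for EFS, for DFS or for the proportion declining Part 2.

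**Time to the first mandated scan.** EOT1 is 30 ± 10 days after surgery, Part 2 week 0 is 21 ± 3 days after EOT1, and the first evaluation is at week 15 (105 ± 10 days).
- Nominal: 30 + 21 + 105 = 156 days after surgery.
- Range: 20 + 18 + 95 = 133 to 40 + 24 + 115 = 179 days.
- All of this imaging lies beyond the Part 2 consent.

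**The passages side by side.**
- Sections 6.1.7 and 9.1.2 (footnote 4): no Part 2 assessment without Part 2 consent, for any patient.
- Section 4: EFS and DFS assessed until all enrolled patients complete follow-up.
- Section 7.3: Table 2, 3 and 4 assessments sought for anyone off study drug who has not withdrawn consent to participate.
- Sections 8.3.5 and 9.1.5.1: patients who stop neoadjuvant drug are followed for recurrence if they have not withdrawn from the study; 9.1.5.1 sends those with R0 or R1 resection to Table 3 and Table 4 imaging.
- Section 9.1: entry to Table 4 follows completion of Table 3.
- Section 9.1.7: survival follow-up starts after Table 4, after recurrence or after incomplete resection.

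A patient who completes neoadjuvant treatment, is resected R0 or R1, declines Part 2 and does not withdraw is named in none of these routes. Section 9.2.4 does seek survival data on all patients who have not withdrawn consent for it.

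**Effect of the censoring rules on that patient, with no EOT1 scan.** DFS is censored on the day of surgery. EFS is censored at the pre-surgical scan, day 75 to 100. Planned follow-up is 4.25 × 365.25 = 1,552 days, so 75/1,552 = 4.8% to 100/1,552 = 6.4% of it is observed. If the patient dies, that death is an event for both endpoints.

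**Illustration 1 (all inputs assumed).** Let d be the proportion declining, with landmark DFS of S_c in consenters and S_d in decliners. If decliners contribute nothing, bias (reported minus true) = d × (S_c − S_d). With S_c = 85%:

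| d | S_d = 60% | S_d = 95% |
|---|---|---|
| 5% | +1.2 points | −0.5 |
| 10% | +2.5 | −1.0 |
| 20% | +5.0 | −2.0 |
| 30% | +7.5 | −3.0 |

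**Illustration 2 (all inputs assumed).** Fix true 2-year DFS at 75%, let decliners have recurrence hazard ratio HR, and solve (1 − d)S + d·S^HR = 0.75 for the reported S.
- d = 15%, HR = 0.5: S = 0.731, bias −1.9 points.
- d = 10%, HR = 2: S = 0.768, bias +1.8.
- d = 15%, HR = 3: S = 0.794, bias +4.4.

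**Allowing for captured deaths.** Assume a quarter of decliners' 2-year events are deaths that are recorded. With q = 0.25 × (1 − S^HR), the reported value becomes (1 − d)S / [(1 − d) + d·q].
- HR = 0.5: q = 0.036; 0.621/0.855 = 0.726, bias −2.4.
- HR = 3: q = 0.125; 0.675/0.869 = 0.777, bias +2.7.

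**Without assumptions.** If nothing is known about decliners, S_d lies between 0 and 1, so the bounds on landmark DFS are d wide: 20 points at 20% declining. For comparison, the 95% half-width for a 75% rate is 1.96 × √(0.75 × 0.25/n), which is 9.7 points at n = 76 and 10.5 at n = 65.

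**The case against.** A reader might infer that EFS and DFS ascertainment stops at surgery for decliners and that the patients still followed are a selected group. The documents do not support that.
- Part 1 runs to EOT1, with a complete physical examination and an optional scan.
- EFS events settled by surgery (progression that precludes it, or no R0 or R1 resection) are captured whatever happens later.
- Deaths count and are sought under Section 9.2.4.
- No decline rate is given, so selection is a risk and not a fact.
- Nothing says how often the EOT1 scan will be done, so it cannot be said that EFS will usually be censored at the pre-surgical scan.

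The wider case against acting is reasonable. The design aims for universal Part 2 consent, and observation with imaging only is one of its options (Section 9.1.6). A patient who refuses even that is close to a study withdrawal, which any consent structure allows. Sections 7.3, 8.3.5 and 9.1.5.1 make non-withdrawal the condition for follow-up, so the consent rule is not a clear bar. The consent forms are not among the documents, and the Part 1 form may already cover recurrence follow-up. EFS and DFS are descriptive summaries in a single arm, with no test or threshold, and the illustrated central bias of +1.8 points is small beside a half-width of about 10.

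These arguments limit the importance of the point and rule out any headline bias figure. They do not remove the gap. The non-withdrawal passages contradict the consent rule without resolving it, and they concern patients off study drug, not expressly those who complete neoadjuvant treatment and then decline Part 2.

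**Conclusion.** The point holds as a gap and an internal conflict. As written, all mandated post-surgical recurrence imaging depends on a consent sought after the surgical outcome is known. That is at odds with Section 4 and with Sections 7.3, 8.3.5 and 9.1.5.1. For a patient who declines Part 2 without withdrawing, recurrence follow-up is undefined. Without an EOT1 scan, ascertainment is then asymmetric: deaths can be counted and recurrences missed, and the censoring may be informative.

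The size and direction of bias cannot be derived from the documents. The illustrations span −3 to +7.5 points of landmark DFS, and rest entirely on assumed decline rates (5% to 30%), DFS levels and hazard ratios. The primary pCR analysis is unaffected. The change is worth making because it is cheap and recurrences not observed usually cannot be recovered later; it does not threaten the trial's main conclusion.

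**What to change.** In the protocol and consent forms:
- Cover post-surgical imaging, recurrence and survival follow-up in the Part 1 consent, if that form does not already do so.
- Limit the Part 2 consent in Section 6.1.7 and Table 3 footnote 4 to adjuvant treatment and its procedures.
- State that declining Part 2 does not end Table 3 and Table 4 imaging follow-up unless the patient withdraws from the study. This also settles the conflict with Sections 7.3, 8.3.5 and 9.1.5.1.

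In the SAP:
- Add to the disposition summary (Section 5.4) the number of patients who decline Part 2, with their pCR status.
- Add a sensitivity analysis of EFS and DFS for this censoring, for example bounds that treat decliners as all recurring or none recurring.

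The cost is a slightly longer Part 1 form, wording changes and a little extra analysis. Patients may still withdraw. For those already past EOT1, the SAP steps remain available.

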6.2. Interim Analysis

No interim analysis is planned for the primary endpoint. After all patients have completed Part 1 of the study ([Table 2](#)), an interim clinical study report (CSR) may be written to describe the analysis results for the primary endpoint. The final CSR will be written to describe the final results of the study, after all patients have had the opportunity to complete Part 2 of the study and post-treatment follow-up ([Table 3](#) and [Table 4](#)).

6.3. Study Committees

Safety oversight for this study will be performed by Regeneron clinical sciences and Pharmacovigilance Risk Management, in collaboration with a contract research organization (CRO).

6.3.1. Independent Central Pathology Review Committee

An independent central pathology review committee will assess pathologic response rate as the primary endpoint for this study. These analyses will be performed in batches, not in real time (clinical decision making will be based on local pathology review). The process for these reviews will be described in a separate charter.

6.3.2. Independent Surgical Committee

An independent surgical committee (ISC) will retrospectively review clinical and imaging data of study patients obtained at the time of enrollment and at completion of neoadjuvant cemiplimab treatment. The ISC will retrospectively recommend a surgical plan, both pre-cemiplimab and post-cemiplimab, based on the available information in each situation, not in real time. The process for ISC reviews will be described in a separate charter.

7. SELECTION, WITHDRAWAL, AND REPLACEMENT OF PATIENTS

7.1. Number of Patients Planned

Approximately 76 patients will be enrolled at approximately 20 global sites.

7.2. Study Population

Patients with stage III to stage IV (M0) CSCC of the head/neck, extremity, or trunk, and selected patients with stage II CSCC (≥ 3 cm longest diameter lesion in an aesthetically-sensitive region), for whom surgery is planned.

7.2.1. Inclusion Criteria

A patient must meet the following criteria to be eligible for inclusion in the study:

1. At least 18 years of age
2. Stage II to IV (M0) CSCC, for which surgery would be recommended in routine clinical practice. For stage II patients, lesion must be ≥ 3 cm at the longest diameter.

Note: Staging is per AJCC 8th edition for HN tumors (Amin, 2017) and is per UICC 9th edition for non-HN tumors (O'Sullivan, 2015).

3. At least 1 lesion that is measurable by RECIST 1.1
4. Eastern Cooperative Oncology Group (ECOG) performance status of 0 or 1

5. Adequate organ and bone marrow function documented by:
 - a. Hemoglobin >9.0 g/dL
 - b. Absolute neutrophil count (ANC) >1.5 x 10⁹/L
 - c. Platelet count >75 x 10⁹/L
 - d. Serum creatinine <1.5 upper limit of normal (ULN) or estimated creatinine clearance (CrCl) >30 mL/min
 - e. Adequate hepatic function:
 - Total bilirubin <1.5 x upper limit of normal (ULN)
 - Aspartate aminotransferase (AST) and alanine aminotransferase (ALT) both <3 x ULN
 - Alkaline phosphatase (ALP) <2.5 x ULN

Note: For patients with Gilbert's syndrome, total bilirubin ≤3x ULN. Gilbert's syndrome must be documented appropriately as past medical history.
6. Willing and able to comply with clinic visits and study-related procedures
7. Willing and able to provide informed consent signed by study patient or legally acceptable representative
8. Able to understand and complete study-related questionnaires

